**Table 17.2-1: Safety Definitions**

Term	Definition
Prolongation of hospitalization	In-patient admission to the hospital that is prolonged beyond the expected standard duration for the condition under treatment.  Note: new adverse events occurring during the hospitalization are evaluated to determine if they prolonged hospitalization or meet another SAE criteria.

**17.3. Relationship to Procedure**

The Investigator must assess the relationship of the reportable SAE to the study procedure. See criteria in Table 17.3-1:

NOTE: Only procedure-related serious adverse events are required to be reported to BSC through the EDC. To avoid administrative errors, the table below has been left in its entirety.

**Table 17.3-1: Criteria for Assessing Relationship of Study Device or Procedure to Adverse Event**

Classification	Description
Not Related Ref: MEDDEV 2.7/3	
Relationship to the device, comparator or procedures can be excluded when:
 
 
- the event is not a known side effect of the product category the device belongs to or of similar devices and procedures;
 
- the event has no temporal relationship with the use of the study device or the procedures;
 
- the serious event does not follow a known response pattern to the medical device (if the response pattern is previously known) and is biologically implausible;
 
- the discontinuation of medical device application or the reduction of the level of activation/exposure - when clinically feasible – and reintroduction of its use (or increase of the level of activation/exposure), do not impact on the serious event;
 
- the event involves a body-site or an organ not expected to be affected by the device or procedure;
 
- the serious event can be attributed to another cause (e.g. an underlying or concurrent illness/ clinical condition, an effect of another device, drug, treatment or other risk factors);
 
- the event does not depend on a false result given by the study device used for diagnosis, when applicable; harms to the subject are not clearly due to use error;
 
- In order to establish the non-relatedness, not all the criteria listed above might be met at the same time, depending on the type of device/procedures and the serious event.
 

Possibly Related Ref: MEDDEV 2.7/3	
The relationship with the use of the study device or comparator, or the relationship with procedures is weak but cannot be ruled out completely. Alternative causes are also possible (e.g. an underlying or concurrent illness/ clinical condition or/and an effect of another device, drug or treatment). Cases where relatedness cannot be assessed or no information has been obtained should also be classified as possible.

Probably Related Ref: MEDDEV 2.7/3	
The relationship with the use of the study device, comparator, or the relationship with procedures seems relevant and/or the event cannot be reasonably explained by another cause, but additional information may be obtained.

**Table 17.3-1: Criteria for Assessing Relationship of Study Device or Procedure to Adverse Event**

Classification	Description
Causal Relationship Ref: MEDDEV 2.7/3	
The serious event is associated with the study device or comparator or with procedures beyond reasonable doubt when:
 
 
- the event is a known side effect of the product category the device belongs to or of similar devices and procedures;
 
- the event has a temporal relationship with the study device use/application or procedures;
 
- the event involves a body-site or organ that 
 
-the study device or procedures are applied to;
 
-the study device or procedures have an effect on;
 
 
 
- the serious event follows a known response pattern to the medical device (if the response pattern is previously known);
 
- the discontinuation of medical device application (or reduction of the level of activation/exposure) and reintroduction of its use (or increase of the level of activation/exposure), impact on the serious event (when clinically feasible);
 
- other possible causes (e.g. an underlying or concurrent illness/ clinical condition or/and an effect of another device, drug or treatment) have been adequately ruled out;
 
- harm to the subject is due to error in use;
 
- the event depends on a false result given by the study device used for diagnosis, when applicable;
 
- In order to establish the relatedness, not all the criteria listed above might be met at the same time, depending on the type of device/procedures and the serious event.
 

**17.4. Investigator Reporting Requirements**

The communication requirements for reporting to BSC are as shown in Table 17.4-1.

**Table 17.4-1: Investigator Reporting Requirements**

Event Classification	Communication Method	Communication Timeline post-market studies* (MEDDEV 2.12/1: GUIDELINES ON A MEDICAL DEVICE VIGILANCE SYSTEM)
Serious Adverse Event	Complete AE eCRF page with all available new and updated information.	
 
• Within 10 calendar days after becoming aware of the event or as per local/regional regulations.
 
• Reporting required through end of study.
 

Event Classification	Communication Method	Communication Timeline post-market studies* (MEDDEV 2.12/1: GUIDELINES ON A MEDICAL DEVICE VIGILANCE SYSTEM)
	Provide all relevant source documentation (de-identified/ pseudonymized) for reported event.	
 
When documentation is available
 
Upon request of sponsor
 

### 17.5. Reporting to Regulatory Authorities / IRBs / Investigators

BSC is responsible for reporting adverse event information to all participating Principal Investigators, IRBs and regulatory authorities, as applicable.

The Principal Investigator is responsible for informing the IRB, and regulatory authorities of SAEs as required by local/regional regulations.

## 18. Informed Consent

Subject participation in this clinical study is voluntary. Informed Consent is required from each subject or his/her legally authorized representative. The Investigator is responsible for ensuring that Informed Consent is obtained prior to any study-required procedures and/or testing, or data collection.

The obtaining and documentation of Informed Consent must be in accordance with the principles of the Declaration of Helsinki, any applicable national regulations, and local Ethics Committee and/or Regulatory authority, as applicable. The ICF must be accepted by BSC or its delegate (e.g., CRO), and approved by the site's IRB, or central IRB, if applicable.

Boston Scientific will provide a study-specific template of the ICF to investigators participating in this study. The ICF template may be modified to meet the requirements of the investigative site's IRB. Any modification requires acceptance from BSC prior to use of the form. The ICF must be in a language understandable to the subject and if needed, BSC will assist the site in obtaining a written consent translation. Translated consent forms must also have IRB approval prior to their use. Privacy language shall be included in the body of the form or as a separate form as applicable.

The process of obtaining Informed Consent shall at a minimum include the following steps, as well as any other steps required by applicable laws, rules, regulations and guidelines:

- be conducted by the Principal Investigator or designee authorized to conduct the process,
- include a description of all aspects of the clinical study that are relevant to the subject's decision to participate throughout the clinical study,
- avoid any coercion of or undue influence of subjects to participate,

- not waive or appear to waive subject's legal rights,
- use native language that is non-technical and understandable to the subject or his/her legal representative,
- provide ample time for the subject to consider participation and ask questions if necessary,
- ensure important new information is provided to new and existing subjects throughout the clinical study.

The ICF shall always be signed and personally dated by the subject or legal representative competent to sign the ICF under the applicable laws, rules, regulations and guidelines and by the investigator and/or an authorized designee responsible for conducting the informed consent process. If a legal representative signs, the subject shall be asked to provide informed consent for continued participation as soon as his/her medical condition allows. The original signed ICF will be retained by the site and a copy of the signed and dated document and any other written information must be given to the person signing the form.

Failure to obtain subject consent will be reported by BSC to the applicable regulatory authority according to their requirements (e.g., FDA requirement is within 5 working days of learning of such an event). Any violations of the informed consent process must be reported as deviations to the sponsor and local regulatory authorities (e.g. IRB), as appropriate.

If new information becomes available that can significantly affect a subject's future health and medical care, that information shall be provided to the affected subject(s) in written form via a revised ICF or, in some situations, enrolled subjects may be requested to sign and date an addendum to the ICF. In addition to new significant information during the course of a study, other situations may necessitate revision of the ICF, such as if there are amendments to the applicable laws, protocol, a change in Principal Investigator, administrative changes, or following annual review by the IRB. The new version of the ICF must be approved by the IRB. Acceptance by Boston Scientific is required if changes to the revised ICF are requested by the site's IRB. The IRB will determine the subject population to be re-consented.

## 19. Committees

### 19.1. Safety Monitoring Process

The BSC personnel from the Medical Safety and Safety Trial Operation group review safety data as it is reported by the sites throughout the duration of the study. During scheduled monitoring activities, clinical research monitors further support this review through their review of source documents and other data information. The BSC Medical Safety and Safety Trial Operations team include health care providers with expertise in oncology and with the necessary therapeutic and subject matter expertise to evaluate and classify the events into the categories outlined above.

## 20. Suspension or Termination

### 20.1. *Premature Termination of the Study*

Boston Scientific, in collaboration with the FDA, reserves the right to terminate the study at any stage but intends to exercise this right only for valid scientific reasons and reasons related to protection of subjects. Investigators, associated IRBs, and regulatory authorities, as applicable, will be notified in writing in the event of study termination.

#### 20.1.1. **Criteria for Premature Termination of the Study**

Possible reasons for premature study termination include, but are not limited to, the following:

- Suspicion of an unacceptable risk, including serious health threat. In this case, the sponsor shall suspend the clinical investigation while the risk is assessed. The sponsor shall terminate the clinical investigation if an unacceptable risk which cannot be controlled is confirmed.
- Instructions by the IRB or regulatory authorities to suspend or terminate the clinical investigation.
- An enrollment rate far below expectation that prejudices the conclusion of the study.

### 20.2. *Termination of Study Participation by the Investigator or Withdrawal of IRB Approval*

Any investigator, or associated IRB or regulatory authority may discontinue participation in the study or withdraw approval of the study, respectively, with suitable written notice to Boston Scientific. Investigators, associated IRBs, and regulatory authorities, as applicable, will be notified in writing in the event of these occurrences.

### 20.3. *Requirements for Documentation and Subject Follow-up*

In the event of premature study termination a written statement as to why the premature termination has occurred will be provided to all participating sites by Boston Scientific. The IRB and regulatory authorities, as applicable, will be notified. Detailed information on how enrolled subjects will be managed thereafter will be provided.

In the event an IRB terminates participation in the study, participating investigators, associated IRBs, and regulatory authorities, as applicable, will be notified in writing. Detailed information on how enrolled subjects will be managed thereafter will be provided by Boston Scientific.

In the event a Principal Investigator terminates participation in the study, study responsibility will be transferred to another investigator, if possible. In the event there are no opportunities to transfer Principal Investigator responsibility, detailed information on how enrolled subjects will be managed thereafter will be provided by Boston Scientific.

The Principal Investigator or his/her designee must return all study-related documents, unless this action would jeopardize the rights, safety, or welfare of the subjects.

#### ***20.4. Criteria for Suspending/Terminating a Study Site***

Boston Scientific reserves the right to stop the inclusion of subjects at a study site at any time after the study initiation visit if no subjects have been enrolled for a period beyond one year after site initiation, or if the site has multiple or severe protocol violations/noncompliance without justification and/or fails to follow remedial actions.

The IRB and regulatory authorities, as applicable, will be notified. Study participants will be contacted, as applicable, and be informed of changes to study visit schedule.

### **21. Study Registration and Results**

#### ***21.1. Study Registration***

If required, to comply with applicable laws and regulations, the study will be registered on a publicly accessible database.

#### ***21.2. Clinical Investigation Report***

Progress reports will be submitted to FDA every six months until enrollment is complete and annually thereafter until the study is complete. Complete study results will be made available in accordance with the legal requirements and the recognized ethical principles, in accordance with the Boston Scientific Policy. A Clinical Investigation Report will be made available to all investigators, IRB and regulatory authorities, as applicable in accordance with the Boston Scientific Policy and local requirements. As applicable an abbreviated Clinical Investigation Report will be made available on a publicly accessible database.

#### ***21.3. Publication Policy***

BSC requires disclosure of its involvement as a sponsor or financial supporter in any publication or presentation relating to a BSC study or its results. BSC may submit study results for publication (regardless of study outcome) following the conclusion or termination of the study. Boston Scientific adheres to the Contributorship Criteria set forth in the Uniform Requirements of the International Committee of Medical Journal Editors (ICMJE; <http://www.icmje.org>). In order to ensure the public disclosure of study results in a timely manner, while maintaining an unbiased presentation of study outcomes, BSC personnel may assist authors and investigators in publication preparation provided the following guidelines are followed:

- All authorship and contributorship requirements as described above must be followed.

- BSC involvement in the publication preparation and the BSC Publication Policy should be discussed with the Coordinating Principal Investigator(s) and/or Executive/Steering Committee at the onset of the project.
- The First and Senior authors are the primary drivers of decisions regarding publication content, review, approval, and submission.

The data, analytic methods, and study materials for this clinical trial may be made available to other researchers in accordance with the Boston Scientific Data Sharing Policy (<https://www.bostonscientific.com/>).

## 23. Abbreviations and Definitions

### 23.1. Abbreviations

Abbreviations are shown in Table 23.1-1.

**Table 23.1-1: Abbreviations**

Abbreviations	Term
AE	Adverse Event
Bq	Becquerel
BSC	Boston Scientific Corporation

Abbreviations	Term
CRF	Case Report Form
CRO	Contract Research Organization
eCRF	Electronic Case Report Form
EDC	Electronic Data Capture
FDA	Food and Drug Administration
Gy	Gray
HCC	Hepatocellular Carcinoma
ICF	Informed Consent Form
IRB	Institutional Review Board
SAE	Serious Adverse Event
SIRT	Selective internal radiation therapy
SPECT	Single Photon Emission Computed Tomography
SPECT-CT	Single Photon Emission Computed Tomography in conjunction with Computed Tomography
Tc-99m MAA	Technetium-99m macroaggregated albumin
Y-90	yttrium-90

### 23.2. Definitions

Terms are defined in **Table 23.2-1**.

**Table 23.2-1: Definitions**

Term	Definition
Complication	An undesirable clinical event that results in death, injury, or invasive intervention. Complications may include, but are not limited to perforation, occlusion, vessel spasm, etc. Complications may or may not be related to the procedure or commercial product.
Source data Ref: ISO 14155	All information in original records, certified copies of original records of clinical findings, observations, or other activities in a clinical investigation, necessary for the reconstruction and evaluation of the clinical investigation Note 1 to entry: This includes source data initially recorded in an electronic format.
Source document Ref: ISO 14155	Original or certified copy of printed, optical or electronic document containing source data.

1 REVISION HISTORY

Document Revision Number	Template Number and Version	Section	Change	Reason for Change
A	90702621 Rev/Ver AF		Initial Document	Initial Release
B	90702621 Rev/Ver AF	Section 2, 3, 4 and 5.3 Listing 16.2.1.2	
• Remove IFU requirement• Remove abbreviations that are not applicable• Change the number of study sites from one to up to three	
• Updates to reflect the change in eligibility criteria in protocol to support study enrollment• Keep consistency with protocol

2 ABBREVIATION

Abbreviation	Description
BMI	Body Mass Index
eCRF	Electronic Case Report Form
FDA	The United States Food and Drug Administration
HCC	Hepatocellular Carcinoma
ICF	Informed Consent Form
ITT	Intention-To-Treat
MedDRA	Medical Dictionary for Regulatory Activities
PAS	Post-Approval Study
PP	Per-Protocol
SAE	Serious Adverse Event
SAP	Statistical Analysis Plan
SIRT	Selective Internal Radiation Therapy
SOC	System Organ Class
Tc-99m MAA	Technetium-99m Macroaggregated Albumin

3 PROTOCOL SUMMARY

TheraSphere is a Y-90 glass microsphere therapy for Selective Internal Radiation Therapy (SIRT) in hepatocellular carcinoma (HCC). Its treatment goal is to selectively target and deliver a tumoricidal radiation dose to tumors within the liver, while maintaining an acceptable radiation dose to the normal liver tissue. The United States Food and Drug Administration (FDA) approved the use of TheraSphere to treat unresectable HCC on March 17, 2021.

Prior to administration of TheraSphere, hepatic arteriography and Technetium-99m macroaggregated albumin (Tc-99m MAA) scanning are performed to detect extrahepatic shunting to the lung or the gastrointestinal tract. At the request of the FDA, the TheraSphere Post-Approval Study (PAS) is being conducted to evaluate the pre-Y-90 radiation-absorbed dose risk of Tc-99m MAA to the whole body and to potential irradiated non-liver critical organs.

TheraSphere PAS is a post-market prospective, single-arm, open-label, observational study. Its primary objective is to calculate the radiation-absorbed dose of Tc-99m MAA to the whole body and to non-liver critical organs. The study will be conducted at up to three clinical study sites in the US, and plans to enroll a total of five patients who are being evaluated for TheraSphere administration.

Study subjects will be required to provide written informed consent prior to any study procedures being conducted. Those who provide written informed consent, fulfill all the inclusion criteria and meet none of the exclusion criteria will be considered enrolled in the study. Subjects enrolled in the study will have 3 images taken after Tc-99m MAA injection: immediately after the injection, 4 hours (within ± 2 hours window) after the injection, and between 18 and 24 hours after Tc-99m MAA injection (Figure 1.1).

[figure not shown]

Figure 1: TheraSphere Post-Approval Study Design

4 INTRODUCTION

The statistical analysis plan (SAP) is based on protocol version B dated 27Oct2022 and the electronic case report form (eCRF) version 4.0 dated 05Dec2022. It will further describe the analysis outlined in the protocol. A mock-up of tables, listings and figures (TLFs) will be provided in this document.

5 GENERAL STATISTICAL METHODS

Continuous data will be summarized with mean, median, standard deviation, quartiles (25th and 75th), minimum and maximum, unless otherwise specified. Categorical data will be summarized with observed counts and percentages for each category. The number and percentage of subjects with missing data will also be provided.

5.1 Analysis Sets

The Intention-To-Treat (ITT) population will comprise of all subjects enrolled in the study that meet eligibility criteria. All analyses will be performed on the ITT population.

The Per-Protocol (PP) population will include all ITT population without any major protocol deviation that could impact the primary endpoint analysis, such as missing SPECT-CT/SPECT scans.

5.2 Control of Systematic Error/Bias

To minimize subject selection bias, all consecutively eligible patients, who provide written informed consent, will be included in the study.

5.3 Number of Subjects per Investigative Site

The study will be conducted at up to three clinical study sites in the US and plans to enroll a total of five subjects.

6 ENDPOINT ANALYSIS

6.1 Primary Endpoint

The endpoints of the study are the mean absorbed doses and delivered activity for whole body and for non-liver critical organs (including whole body effective dose). Non-liver critical organs include lungs, salivary gland, thyroid gland, stomach mucosa/wall, gallbladder wall, small intestine mucosa/wall, colon mucosa/wall, urinary bladder wall, kidneys, spleen, and heart wall.

Tc-99m MAA activity is measured through SPECT-CT/SPECT scans immediately after the injection, 4 hours (within ± 2 hours window) after the injection, and between 18 and 24 hours after the injection. For each organ, a plot of activity and time from Tc-99m MAA administration will be constructed, and an appropriate graphing software will be used to fit a curve to the data. The cumulative activity (area under the curve) divided by the administered activity will be used as an input to S-value-based dosimetry software to determine absorbed dose and effective absorbed dose.

Descriptive statistics will be used to summarize delivered activity for whole body and for non-liver critical organs at post-Tc-99m MAA injection, 4 hours after the injection and 18-24 hours after the injection. Descriptive statistics will be also used to summarize the mean absorbed dose and effective dose for whole body and for non-liver critical organs.

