## Patient Exposure Study

Primary Endpoints	Mean absorbed dose (Gy) and activity (Bq) will be summarized for the whole body and for critical non-liver organs (including whole body effective dose).
Follow-up Schedule	
At a minimum, all patients will be evaluated at the following timepoints:
 
 
• Immediately following Tc-99m MAA injection
 
• 4 hours <math>\pm</math> 2 hours after Tc-99m MAA injection
 
• <math>\geq</math> 18 hours after Tc-99m MAA injection but <math>\leq</math> 24 hours after Tc-99m MAA injection
 
 
At each evaluation timepoint, the following images will be performed:
 
 
• Immediately following Tc-99m MAA injection: Single Photon Emission Computed Tomography in conjunction with Computed Tomography (SPECT-CT)
 
• All other images: Single Photon Emission Computed Tomography (SPECT)
 
 
The start of the study for each eligible patient will be immediately after signed written informed consent. The study will be considered complete after five patients have completed three post-Tc-99m MAA imaging assessments.

Study Duration	Enrollment is expected to be completed within 24 months; therefore, the total study duration is estimated to be 24 months.
Participant Duration	The study duration for each subject is expected to be up to 24 hours.
Inclusion Criteria	
 
1. Patients 21 years and older
 
2. Patient written informed consent
 
3. Patients who receive Tc-99m MAA while being evaluated for TheraSphere treatment
 

Exclusion Criteria	
 
1. Patients who are contraindicated for TheraSphere treatment
 
2. Patients who are contraindicated for Tc-99m MAA per the applicable Package Insert
 
3. Patients who do not receive Tc-99m MAA during pre-treatment Y-90 mapping
 

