### **11.1. Primary Endpoints**

The endpoints of the study are the mean absorbed doses and delivered activity for whole body and for critical organs (including whole body effective dose). The mean and standard deviation will be summarized for each of these.

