11 TABLES AND LISTINGS SHELLS

This section will give the format and structure of all tables and listings to be produced. These detailed specifications can undergo minor revisions during the production phase without needing to revise the SAP. Minor revisions are defined as revisions that do not invalidate any of the specifications in this SAP.

Table 14.1.1 Subject Disposition – All Subjects

	Subjects
Patients Screened	xx
Populations, n (%)	
ITT ^a	xx (xx.x)
PP ^b	xx (xx.x)
Study Status, n (%)^c	
Subject completed the study	xx (xx.x)
Investigator withdrawal	xx (xx.x)
Subject withdrawal	xx (xx.x)
Subject died	xx (xx.x)
Other	xx (xx.x)

^a ITT is defined as subjects who were enrolled and meet the eligibility criteria.

^b PP is defined as ITT subjects without any major protocol deviation, such as missing SPECT-CT/SPECT scans.

^c Percentages are based on the number of subjects in the ITT population

Table 14.2.1 Primary Endpoint Summary – ITT Population

ITT Population (N=XX)	
Delivered Activity for Whole Body (MBq)	
Immediately following	
n	xx
Mean (SD)	xx (xx.x)
Median	xx
Q1, Q3	xx, xx
Min, Max	xx, xx
4 hours +/- 2 hours	
n	xx
Mean (SD)	xx (xx.x)
Median	xx
Q1, Q3	xx, xx
Min, Max	xx, xx
18-24 hours	
n	xx
Mean (SD)	xx (xx.x)
Median	xx
Q1, Q3	xx, xx
Min, Max	xx, xx
Delivered Activity for Non-Liver Critical Organs (MBq)	
Immediately following	
n	xx
Mean (SD)	xx (xx.x)
Median	xx
Q1, Q3	xx, xx
Min, Max	xx, xx
4 hours +/- 2 hours	
n	xx
Mean (SD)	xx (xx.x)
Median	xx
Q1, Q3	xx, xx
Min, Max	xx, xx
18-24 hours	
n	xx
Mean (SD)	xx (xx.x)
Median	xx
Q1, Q3	xx, xx
Min, Max	xx, xx
Absorbed Dose (Gy) – Whole Body	
n	xx
Mean (SD)	xx (xx.x)
Median	xx
Q1, Q3	xx, xx
Min, Max	xx, xx

ITT Population (N=XX)	
Absorbed Dose (Gy) – Non-Liver Critical Organs	
n	xx
Mean (SD)	xx (xx.x)
Median	xx
Q1, Q3	xx, xx
Min, Max	xx, xx
Effective Dose (mSv) – Whole body	
n	xx
Mean (SD)	xx (xx.x)
Median	xx
Q1, Q3	xx, xx
Min, Max	xx, xx
Effective Dose (mSv) – Non-Liver Critical Organs	
n	xx
Mean (SD)	xx (xx.x)
Median	xx
Q1, Q3	xx, xx
Min, Max	xx, xx

Programming note: delivered activity for non-liver critical organs is the sum of all the individual activity for non-liver critical organs including others. The same thing is applied to absorbed dose and effective dose.

Listing 16.2.1.1 Disposition – All Subjects

Subject ID	ITT Population	PP Population	Consent Date	Version of ICF	End of Study Date	End of Study Reason
xxxxxxxx	Yes	Yes	ddMMMyyyy	xx.xx	ddMMMyyyy	xxxxx

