xxxxxxxx	No	No				Other: specify

Listing 16.2.1.2 Inclusion/Exclusion – All Subjects

Site #	Subject ID	Meet Eligibility?	Inclusion Criteria Not Met	Exclusion Criteria Met
xx	xxxxxxxx	Yes		
xx	xxxxxxxx	No	Inclusion 1: Patients 21 years and older; Inclusion 3: Patients who receive Tc-99m MAA while being evaluated for TheraSphere treatment	Exclusion 2: Patients who are contraindicated for Tc-99m MAA per the applicable Package Insert

Listing 16.2.1.3 Demographics – ITT population

Subject ID	Age at Consent (years)	Gender at birth	Race	Ethnicity	Height (unit)	Weight (unit)	BMI (kg/m ²) ^a	HCC Diagnosis Date for Current Treatment	Months since Diagnosis
XXXXXXXXXX	xx	xx	xx	xx	xx (cm)	xx (kg)	xx	ddMMMyyyy	xx.x
XXXXXXXXXX	xx	xx	xx	xx	xx (in)	xx (lb)	xx	ddMMMyyyy	xx.x

^aBMI is calculated as weight (kg)/height (m)²

Listing 16.2.1.4 Protocol Deviations – ITT population

Subject ID	Date of Deviation	Folder /Form	Category	Reason
xxxxxx	ddMMMyyyy		Other: specify	
xxxxxx	ddMMMyyyy		Event not reported per protocol: AE number	

Listing 16.2.2.1 Tc-99m MAA Administration – ITT population

Subject ID	Date of Administration	Time of Administration	Vascular Access	Tc-99m MAA activity in syringe before injection (unit)	Tc-99m MAA injection volume (cc)	Tc-99m MAA activity remaining in syringe (unit)	Location of Tc-99m MAA injection
xxxxxxx	ddMMMyyyy	xx:xx	Femoral Artery	xx (mBq)	xx	xx (mBq)	List all the locations
xxxxxxx	ddMMMyyyy	xx:xx	Radial Artery	xx (mBq)	xx	NA	
xxxxxxx	ddMMMyyyy	xx:xx	Femoral Artery	xx (mCi)	xx	xx (mCi)	

Listing 16.2.2.2 Imaging Information – ITT population

Subject ID	Time from Tc-99m MAA Administration	Image Modality	Date of Image	Time of Image
xxxxxxxx	Immediately following	SPECT-CT	ddMMMyyyy	xx:xx
	4 hours +/-2 hours	SPECT	ddMMMyyyy	xx:xx
	18-24 hours	SPECT	ddMMMyyyy	xx:xx
xxxxxxxx	Immediately following	SPECT-CT	ddMMMyyyy	xx:xx
	4 hours +/-2 hours	SPECT	ddMMMyyyy	xx:xx
	18-24 hours	SPECT	ddMMMyyyy	xx:xx

Listing 16.2.2.3 Tc-99m MAA Deposition – ITT population

Subject ID	Region	Volume (cc)	Activity (MBq)			Absorbed Dose (Gy)	Effective Dose (mSv)
			Immediately following	4 hours	+/- 2 hours		
XXXXXXXXXX	Liver	xx	xx		xx	xx	xx
	Lungs	xx	xx	xx		xx	xx
	Salivary gland	xx	xx	xx		xx	xx
	Thyroid gland	xx	xx	xx		xx	xx
	Stomach mucosa/wall	xx	xx	xx		xx	xx
	Gallbladder wall	xx	xx	xx		xx	xx
	Small intestine mucosa/wall	xx	xx	xx		xx	xx
	Colon mucosa/wall	xx	xx	xx		xx	xx
	Urinary bladder wall	xx	xx	xx		xx	xx
	Kidneys	xx	xx	xx		xx	xx

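### The SAP puts an undefined effective dose, summed over organs, into the primary table, although the protocol and the SAP's own endpoint definition name effective dose for the whole body only

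*SAP*

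**What the plan says.** Three statements of the endpoint agree. The protocol synopsis gives dose and activity for "whole body and for critical non-liver organs (including whole body effective dose"). Protocol 11.1 has "for whole body and for critical organs (including whole body effective dose"), and the first sentence of SAP 6.1 has "for whole body and for non-liver critical organs (including whole body effective dose"). In each, absorbed dose and activity apply to the whole body and the organs, and the only effective dose mentioned is that of the whole body.

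The SAP then goes further in three places:

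- The last sentence of SAP 6.1 will "summarize the mean absorbed dose and effective dose for whole body and for non-liver critical organs".
- Table 14.2.1 (SAP 11) has a row "Effective Dose (mSv) – Non-Liver Critical Organs" next to the whole-body effective dose row. The programming note below the table says that "delivered activity for non-liver critical organs is the sum of all the individual activity for non-liver critical organs including others", and continues: "The same thing is applied to absorbed dose and effective dose".
- The listing titled "Listing 16.2.2.3 Tc-99m MAA Deposition – ITT population" has an effective dose column in mSv covering every region: the liver, the 11 named non-liver organs, three lines for other regions, and the whole body.

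SAP 6.1 obtains the doses from S-value-based software that it does not name. There it uses a further term, effective absorbed dose, also without definition. Neither document gives a set of tissue weights.

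**The concern.** The SAP tells the programmer to print, in the primary table, a quantity that lies outside the stated endpoint and that neither document defines. Two constructions fit the instruction:

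- **Reading A:** the organ's equivalent dose with no tissue weighting. The row is then a plain sum of organ doses expressed in mSv.
- **Reading B:** the organ's tissue-weighted contribution to the whole-body value. The row is then the part of the whole-body effective dose that comes from these organs.

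Both carry the unit mSv and would print under the same label. Under A, the row for part of the body can exceed the whole-body effective dose in the same table. Under B, it is a component of that figure. The study was requested by the FDA to quantify these doses and is purely descriptive, so the dose tables are its result. A primary row that cannot be interpreted from the plan is a defect in the deliverable.

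**Working it through.** **1. What the documents settle.** The synopsis, Protocol 11.1 and the first sentence of SAP 6.1 against the last sentence of SAP 6.1, Table 14.2.1 and Listing 16.2.2.3: the first group names effective dose for the whole body, the second adds the organs. This mismatch needs no outside input. There is no stated figure to reproduce, because the documents give no organ doses and no weights.

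**2. Inputs for the size.** From SAP 6.1: 11 named organs (lungs, salivary gland, thyroid, stomach, gallbladder, small intestine, colon, urinary bladder, kidneys, spleen, heart). Everything else is assumed:

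- Effective dose has its usual meaning, a sum over tissues of weight × equivalent dose, with the weights over all tissues adding to 1.
- The radiation weighting factor is 1, so 1 mGy corresponds to 1 mSv of equivalent dose.
- Weights *w*: 0.12 each for lungs, stomach and colon; 0.04 each for thyroid and bladder; 0.01 for salivary glands; 0.12/13 = 0.00923 each for the other five.
- Other regions are left out, since the documents do not say what they will be.

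**3. Formula.** With organ doses *D*, reading A is Σ*D* and reading B is Σ*wD*. The ratio is Σ*D* / Σ*wD*, which is 1 divided by the dose-weighted average of the weights.

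**4. Equal doses, 1 mGy in each organ.**

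- A: 11 × 1 = 11 mSv.
- B: 3(0.12) + 2(0.04) + 0.01 + 5(0.12/13) = 0.36 + 0.08 + 0.01 + 0.046 = 0.496 mSv.
- Ratio: 11 / 0.496 = 22.2.

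If every tissue in the body received 1 mGy, the whole-body effective dose would be 1 mSv. Reading A would print 11 mSv beside it; reading B would print about 0.50 mSv.

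**5. Other dose patterns.** Because the ratio is the reciprocal of an average weight, it must lie between 1/0.12 and 1/(0.12/13).

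| Pattern | Ratio |
|---|---|
| All dose in lungs, stomach or colon | 1/0.12 = 8.3 |
| All dose in thyroid or bladder | 1/0.04 = 25 |
| All dose in salivary glands | 1/0.01 = 100 |
| All dose in one of the other five | 13/0.12 = 108 |
| Lungs at 10 times the others | 20 / (0.496 + 9 × 0.12) = 12.7 |
| Kidneys at 10 times the others | 20 / (0.496 + 9 × 0.00923) = 34.5 |
| 200,000 random patterns (Dirichlet, parameter 1) | median 22.8, 95% range 13.4 to 44.8 |

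**6. Sensitivity to the weights.** A second assumed set has 0.12 for lungs, stomach and colon; 0.05 for thyroid and bladder; 0.005 for small intestine, kidneys and spleen; and 0 for the other three. It sums to 0.36 + 0.10 + 0.015 = 0.475 and gives 11/0.475 = 23.2 for equal doses. The lower limit stays at 8.3. There is no finite upper limit, because some weights are zero.

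**The case against.** The best case against the point is that it needs no more than a footnote. The whole-body effective dose, which is what the protocol asks for, has its own row and does not depend on the organ row. Listing 16.2.2.3 prints absorbed dose in Gy for each region beside the mSv column, so organ dose is available under its own name. If the mSv column turned out to be exactly 1000 times the Gy column, a reader could tell that reading A had been used. The study has five patients and no test or decision rule, and SAP 11 allows minor changes to the shells without a revision.

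Most of this stands, and it limits the consequence. It does not remove the defect. Working out afterwards which quantity was printed is no substitute for specifying it, and a footnote would leave in the primary table a row that the endpoint definition does not include. The extension is also in the text of SAP 6.1, not only in a shell.

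A reader might infer four stronger things that the documents do not support:

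- *That the SAP carries a 20-fold error.* The 22-fold figure needs weights from outside the documents and equal organ doses. The biodistribution series described in Protocol 5 found uptake in the renal cortex in 100% of patients, gastric mucosa in 46%, and thyroid and salivary glands in 33% each. Those are frequencies and not doses, but they do not suggest equality.
- *That the primary row reports individual organs.* It is one pooled sum; values by organ appear only in the listing.
- *That any organ-level figure is illegitimate.* The documents show only that the term is undefined and outside the endpoint. A correctly labelled weighted contribution would be acceptable.
- *That the organ absorbed doses are compromised.* The values by organ in the listing are not touched by this point.

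**Conclusion.** The point holds as an inconsistency with an undefined quantity. The SAP extends effective dose from the whole body to the organs, against Protocol 11.1, the synopsis and its own endpoint definition, and then sums it over organs in the primary table without saying what is summed. That much rests on the documents alone.

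The size is conditional. Under the main assumed weight set, the two readings of the pooled row differ about 22-fold for equal organ doses and by about 8 to 108 across all dose patterns. Even the lower limit would change how the row is read. Whether the row exceeds the whole-body value depends on the reading and on the organ doses: it can under the unweighted reading, and under the weighted reading it is only a part of the whole. The effect is confined to interpretation of one descriptive row and one listing column.

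**What to change.** Align the SAP with Protocol 11.1 by reporting effective dose for the whole body only:

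- In the last sentence of SAP 6.1, keep absorbed dose for whole body and organs, and restrict effective dose to the whole body. Replace or define the term effective absorbed dose.
- In Table 14.2.1, delete the pooled non-liver effective dose row and take effective dose out of the summing note.
- In Listing 16.2.2.3, print effective dose on the whole-body line only.

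If organ values are wanted, print them per organ in the listing under the label *contribution to effective dose (tissue weight × equivalent dose)*. State the weight set, and leave the entry blank for any other region to which that set gives no weight.

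The cost is wording in the SAP and its shells, and the loss of one row that the protocol does not ask for. SAP 8 already provides the route: an amended SAP if the analyses have not been run, or a reasoned note in the clinical study report if they have.
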